12.2. Adverse and Serious Adverse Events

12.2.1. Definition of Adverse Events

12.2.1.1. Adverse Event (AE)

Adverse Event (AE): Any untoward medical occurrence associated with the use of an investigational product in humans, whether or not considered drug related.

Adverse Reaction (AR): any AE caused by a drug. Adverse reactions are a subset of all suspected adverse reactions where there is reason to conclude that the drug caused the event.

Suspected Adverse Reaction (SAR):

Any AE for which there is a reasonable possibility that the drug caused the AE. For the purposes of IND safety reporting, “reasonable possibility” means there is evidence to suggest a causal relationship between the drug and the AE. A SAR implies a lesser degree of certainty about causality than adverse reaction, which means any AE caused by a drug.

Unexpected: An AE or SAR is considered “unexpected” if it is not listed in the Investigator’s Brochure or is not listed at the specificity or severity that has been observed; or, if an Investigator’s Brochure is not required or available, is not consistent with the risk information described in the general investigational plan or elsewhere in the current application.

Life-threatening: An AE or SAR is considered “life-threatening” if, in the view of either the Investigator or Sponsor, its occurrence places the subject or subject at immediate risk of death. It does not include an AE or suspected adverse reaction that, had it occurred in a more severe form, might have caused death.

12.2.1.2. Serious Adverse Event (SAE)

A SERIOUS ADVERSE EVENT (SAE) is any AE or suspected adverse reaction occurring at any dose that:

- Results in death.
- Is life-threatening.
- Results in a persistent or significant incapacity or substantial disruption of the ability to conduct normal life functions.
- Requires in subject hospitalization.
- Prolongs in subject hospitalization.
- Is a congenital anomaly/birth defect.
- Is a significant medical event (i.e., one that may jeopardize the subject or may require intervention to prevent one or more of the other outcomes listed above).

A NON-SERIOUS ADVERSE EVENT is any AE that does not meet the definitions for SAEs as described above.

Each AE will be classified as **SERIOUS or NON-SERIOUS** using the definitions provided above.

12.3. Relationship to Investigational product

The **SEVERITY** of each AE will be classified as **MILD, MODERATE, or SEVERE**.

The Investigator will review each event and assess its **RELATIONSHIP** to use of investigational product (unrelated, unlikely, possibly, probably, definitely). The AE will be assessed using the following definitions:

Unrelated:

- Event occurring before dosing.
- Event or intercurrent illness due wholly to factors other than investigational product use.

Unlikely:

- Poor temporal relationship with investigational product use.
- Event easily explained by subject's clinical state or other factors.

Possibly:

- Reasonable temporal relationship with investigational product use.
- Event could be explained by subject's clinical state or other factors.

Probably:

- Reasonable temporal relationship with investigational product use.
- Likely to be known reaction to agent or chemical group, or predicted by known pharmacology.
- Event cannot easily be explained by subject's clinical state or other factors.

Definitely:

- Distinct temporal relationship with investigational product use.
- Known reaction to agent or chemical group, or predicted by known pharmacology.
- Event cannot be explained by subject's clinical state or other factors.

12.4. Recording Adverse Events

AEs will be monitored throughout the study (from the time of ICF signature through Visit 4) and will be recorded on the eCRF with the date and time of onset, date and time of resolution, severity, seriousness, causality (relationship to use of investigational product), treatment required, and the outcome.

To elicit AEs, simple questions with minimal suggestions or implications should be used as the initial questions at all evaluation points during the trial. For example:

How have you felt since your last assessment?

Have you had any health problems since your last assessment?

The severity of each AE should be categorized as mild, moderate, or severe.

The causality of use of investigational product in relation to the AE will be assessed by the Principal Investigator after careful medical consideration and categorized as unrelated, unlikely, possible, probable, or definite.

If an AE occurs, the Investigator will institute support and/or treat as deemed appropriate. If a non-SAE is unresolved at the time of the last day of the study, an effort will be made to follow up until the AE is resolved or stabilized, the subject is lost to follow-up, or there is some other resolution of the event. The Investigator should make every attempt to follow SAEs to resolution.

12.5. Reporting Adverse Events

Serious Adverse Event Reporting

It is the responsibility of the Investigators or their designees to report any event of this nature to the Sponsor or a designee within 24 hours of the event being brought to the Investigators' or their staffs' attention. It is also the responsibility of the Investigator to report all SAEs reported at their site to their Institutional Review Board (IRB), as required. The Investigator should make every attempt to follow all SAEs to resolution.

The following information should be provided when an SAE is reported to the Sponsor or designee:

1. Protocol Number
2. Site Number
3. Subject Number
4. Subject Demographic information, including:
 - Date of Birth
 - Sex
 - Race
5. Investigational product start date
6. Date of last dose of investigational product
7. Date investigational product reinitiated (if investigational product interrupted)
8. SAE information, including:
 - SAE term (diagnosis only; if known or serious signs/symptoms)
 - Description of SAE/narrative

- Date/time of onset
- Severity
- Outcome
- Date/time of resolution or death (if duration < 24 hours)
- Relationship to investigational product
- Action taken with investigational product

9. Criteria for classifying the event as serious, including whether the SAE:

- Resulted in death.
- Was life-threatening
- Required inpatient hospitalization.
- Prolonged inpatient hospitalization.
- Resulted in a persistent or significant incapacity or substantial disruption of the ability to conduct normal life functions.
- Was a congenital anomaly/birth defect.
- Important medical events that may not result in death, were not life-threatening, or did not require hospitalization may be considered serious when, based upon appropriate medical judgment, they may jeopardize the subject or subject and may require medical or surgical intervention to prevent one of the outcomes listed in this definition. Examples of such medical events include allergic bronchospasm requiring intensive treatment in an emergency room or at home, blood dyscrasias or convulsions that do not result in subject hospitalization, or the development of drug dependency or drug abuse.

10. Concomitant medications

11. Relevant history

12. Possible causes of SAE other than investigational product

13. Copy of AE page from the eCRF

NOTE: If an SAE occurs in any study involving KPI-121 0.25% ophthalmic suspension that is unexpected and is determined to be related or possibly related to investigational product, all sites will be notified by the Sponsor and each site should report it to its IRB.

13. STATISTICS

Continuous measures (e.g., age) will be summarized descriptively by the mean, standard deviation, median, minimum and maximum values. Categorical measures will be summarized by the number and percent of subjects.

13.1. Subject Demographics, Disposition and Background variables

Subject disposition, demographic characteristics, and background variables will be summarized by study group.

13.2. Analysis of Efficacy

13.2.1. Primary Efficacy Analyses

The primary analysis population will be the Intent-to-Treat (ITT) population, defined as all randomized subjects who received at least one dose of randomized investigational product. A subset of efficacy analyses will be examined for the Per Protocol (PP) population, the definition of which will be outlined in the Statistical Analysis Plan (SAP) and finalized prior to unmasking of study data pursuant to clinical data review. The specific details of endpoint testing will be elaborated in the SAP. If changes to the Statistical Analysis elaborated in the protocol are deemed necessary, those changes will be made prior to unmasking the study data and may only be elaborated in the Statistical Analysis Plan.

The trial will have 2 primary endpoints each tested at [REDACTED]:

1. Change in ODS scores in the ITT population [REDACTED]
[REDACTED]
2. Change in ODS scores in the ITT subgroup with more severe baseline ocular discomfort [REDACTED]
[REDACTED]
[REDACTED]
[REDACTED]
[REDACTED]
[REDACTED]
[REDACTED]
[REDACTED]

13.2.2. Secondary Efficacy Analyses

Secondary efficacy endpoint comparisons will be performed between KPI-121 0.25% ophthalmic suspension group and the vehicle group [REDACTED] if the null hypotheses for the primary endpoints are rejected. The secondary endpoints testing will be [REDACTED]
[REDACTED]:

1. Change from baseline (Day 1) in bulbar conjunctival hyperemia scores in the ITT population at Visit 4 (Day 15 + 2 days)
[REDACTED] in the study eye [REDACTED]
[REDACTED].
2. Change from baseline (Day 1) in bulbar conjunctival hyperemia scores in the ITT population at Visit 4 (Day 15 + 2 days)
[REDACTED].
3. Change in ODS scores in the ITT population
[REDACTED]
[REDACTED].
4. Change from baseline (Day 1) in [REDACTED] corneal fluorescein staining scores in the ITT population at Visit 4 (Day 15 + 2 days) in the study eye.
5. Change in ODS scores in the ITT population
[REDACTED]
[REDACTED].

13.2.3. Exploratory Efficacy Analyses

Exploratory efficacy endpoints will be evaluated.

13.3. Analysis of Safety

Analysis of safety data will be presented for all subjects in the Safety population (i.e., all randomized subjects receiving at least one dose of randomized investigational product and from whom at least one safety assessment is obtained after randomization). AEs will be coded using Medical Dictionary for Regulatory Activities (MedDRA, most current version) and categorized by system organ class using preferred terms. AEs will be tabulated by study group with respect to their Severity and relationship to the investigational product. Ophthalmoscopy findings will be summarized descriptively. IOP measurements, BCVA and Biomicroscopy will be summarized as safety outcomes.

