21. Have a history of ocular allergies, which, in the judgment of the investigator, are likely to have an acute increase in severity due to the expected timing of exposure to the allergen to which the subject is sensitive. Subjects sensitive to seasonal allergens that are not expected to be present during the study are permitted.

22. Have been exposed to an investigational product within **30 days** prior to Visit 1 (Screening).

23. Be an employee of the practice that is involved in the management, administration, or support of this study or be an immediate family member of the same.

24. Have a documented history of alcohol and/or drug abuse.

25. In the opinion of the Investigator or study coordinator, be unwilling or unable to comply with the study protocol or unable to successfully instill eye drops.

- 26. Have used any marijuana products for 72 hours prior to Visit 1 (Screening) and for the duration of the study.
- 27. Have been randomized for participation in KPI-121-C-006 (STRIDE 1) or KPI-121-C-007 (STRIDE 2).

Investigational product, dosage and mode of administration: KPI-121 0.25% ophthalmic suspension

Dosage and duration of treatment: 1 to 2 drops of investigational product will be instilled in each eye four times per day (QID) for approximately 14 days.

Reference therapy (Comparator), dosage and mode of administration: KPI-121 0.25% ophthalmic vehicle will be supplied as investigational product.

Efficacy assessments:

- Subject-rated assessment of ocular discomfort [REDACTED]
- [REDACTED] assessment of bulbar conjunctival hyperemia
- [REDACTED]
- [REDACTED] corneal fluorescein staining
- Subject-rated assessment of eye dryness

Safety assessments:

- Assessment of adverse events (AEs)
- Slit lamp biomicroscopy
- IOP measurement
- BCVA
- Dilated Ophthalmoscopy
- Pregnancy screen (performed only at Visits 1 and 4)

Statistical methods:

[figure not shown]
All primary efficacy endpoint comparisons will be performed between the KPI-121 0.25% ophthalmic suspension group and the vehicle group [REDACTED]. The specific details of endpoint testing will be elaborated in the Statistical Analysis Plan (SAP).

Primary Efficacy Analyses:

The trial will have 2 primary endpoints [REDACTED] ;

1. Change in ODS scores in the ITT population [REDACTED]

2. Change in ODS scores in the ITT subgroup with more severe baseline ocular discomfort

Secondary Efficacy Analyses:

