7. INVESTIGATIONAL PLAN

7.1. Overall Study Design

This is a Phase 3, multicenter, double-masked, randomized, vehicle-controlled, parallel-group study designed to evaluate the safety and efficacy of KPI-121 0.25% ophthalmic suspension in treating the signs and symptoms of dry eye disease.

This study will include up to 4 clinic visits, including 2 weeks of single-masked vehicle in Stage 1 followed by approximately 14 days of investigational product dosing (KPI-121 0.25% ophthalmic suspension or vehicle in Stage 2).

Approximately 3200 subjects at approximately 80 centers located in the United States (US) will be screened at Visit 1 (Screening). Subjects meeting eligibility criteria at this visit will enter a 14-day Stage 1 period of QID dosing with single masked vehicle. At Visit 2 (Day 1/Randomization), approximately 900 subjects who continue to meet eligibility criteria will be randomized in an approximate 1:1 ratio to either KPI-121 0.25% ophthalmic suspension or vehicle dosed QID. Subjects will be allocated in an approximate 1:1 ratio at each site.

Study qualification criteria will be entered into the Interactive Web Response System (IWRS) for stratification at randomization. Other randomization and stratification allocation criteria will be applied as elaborated in the data management plan. Randomization numbers will be automatically assigned to each subject as they are entered into the IWRS based on stratification criteria.

To minimize bias, investigational product allocation (KPI-121 0.25% ophthalmic suspension versus vehicle) will be randomized and masked to the Sponsor, subjects, and the investigative staff with the exception of a dosing coordinator. The dosing coordinator will be responsible for dispensing and retrieving investigational product to/from subjects, instructing subjects regarding dosing of the investigational product, addressing study subjects' questions regarding investigational product, [REDACTED]. As a consequence of these interactions, the dosing coordinator has the potential for being unmasked to the study treatment for each subject. The randomization schedule will be generated by the randomization statistician (who is not on the project team) or designee and maintained in a secure and limited-access location separate from the study Investigator and members of the project team.

[figure not shown]

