7.4. Visit Description

7.4.1. Visit 1: 14 ± 1 Days Prior to Day 1 – Screening

After obtaining written informed consent and HIPAA authorization, site staff will perform/assess the following in the order suggested below. Each subject that is screened will be assigned a Subject Identification (ID) consisting of a 5-digit Investigator number plus a 3-digit Subject number. The Subject ID will be used as the primary subject identifier for the duration of the study.

- Subject-rated assessment of ocular discomfort as graded by the subject [REDACTED]
[REDACTED]
- Significant non-ocular and significant ocular medical history
- Concomitant medication usage and medications taken during the 6 months prior to screening
- Inclusion/exclusion criteria
- Urine pregnancy test (UPT) for WOCBP
- BCVA
- [REDACTED] assessment of bulbar conjunctival hyperemia
- Slit Lamp Biomicroscopy
- Corneal fluorescein staining
- Unanesthetized Schirmer Test evaluation
- IOP measurement
- Dilated Ophthalmoscopy
- Single-masked, investigational product instillation
- AE Assessment

- Dispense single masked, investigational product and instructions for administration
 - The first dose of single-masked investigational product will be administered in the clinic under the supervision of a designated dosing coordinator. This dosing coordinator, who is not responsible for study assessments, will also be required to dispense and retrieve investigational product to/from the subjects, provide instruction to the subjects regarding dosing of the investigational product, address study subjects' questions regarding the investigational product, [REDACTED]. Prior to administration of investigational product, subjects will be instructed regarding proper method for instillation of investigational product including but not limited to shaking investigational product bottle prior to each instillation. Since subjects will receive 1 dose of investigational product in the clinic, they will self-administer at most 3 additional doses of investigational product on the first day.
 - [REDACTED]

Instructions to subject:

- Dose single-masked Stage 1 investigational product as instructed
- [REDACTED]
- [REDACTED]
- Return for Visit 2 scheduled in 14 ± 1 days.

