10.2. Investigational product Packaging and Labeling

The Stage 1 investigational product will be 1 bottle of single-masked, investigational product (vehicle) from a common site level supply which will be provided to the subject after qualifying for Stage 1. The bottle labels for the single-masked period contain the following information: Sponsor name, protocol number, lot number, unique identifying number, storage temperature, and required statement(s) per the FDA requirements.

The randomized investigational product kit will consist of a box containing 2 dropper bottles of investigational product. At Day 1, eligible subjects will receive 1 bottle of investigational product. The second bottle will be retained at the site and provided to the subject in the event the subject needs additional investigational product during the treatment period. The box label and dropper bottle labels will contain the following information: Sponsor name, protocol and kit number, storage temperature, and required statement(s) per the FDA requirements.

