10.5. Administration

At Visits 1 and 2, when subjects receive the first dose in the clinic, that dose will count as 1 of their 4 (QID) daily doses. Subjects will then self-administer at most 3 additional doses of investigational product during the remainder of that day to complete QID dosing. All visits should be scheduled in the morning to allow subjects to receive a full day of QID dosing. Any Stage 1 doses taken on the morning of Visit 2 should be counted into the total 4 doses for the day.

Subjects will be asked to instill 1 dose upon awakening and then 3 subsequent doses approximately 4 hours after their previous dose. The 4 doses will be described as “Morning Dose,” “Mid-Morning Dose,” “Afternoon Dose,” and “Evening Dose.”

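### Are run-in adverse events left ambiguous because the plan does not name the first dose that counts for relatedness and for the by-arm tables?

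*Combined protocol and SAP*

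**What the plan says.** Adverse events are collected over both stages. Section 12.4 states: "AEs will be monitored throughout the study (from the time of ICF signature through Visit 4". Section 12.3 lists "Event occurring before dosing" as one of two grounds for grading an event unrelated. Section 13.3 then plans the tables: "AEs will be tabulated by study group with respect to their Severity and relationship to the investigational product". It gives no rule on onset date. Its Safety population requires a dose of randomized product and a safety assessment after randomization.

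The term investigational product appears in two settings.

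- For the randomized period. Section 7.1 describes "2 weeks of single-masked vehicle in Stage 1 followed by approximately 14 days of investigational product dosing". The synopsis gives the dosage as "1 to 2 drops of investigational product will be instilled in each eye four times per day (QID) for approximately 14 days".
- For the run-in vehicle as well. Section 7.4.1 says: "The first dose of single-masked investigational product will be administered in the clinic under the supervision of a designated dosing coordinator". Section 10.2 says: "The Stage 1 investigational product will be 1 bottle of single-masked, investigational product (vehicle". Section 10.5 speaks of a first dose at two visits: "At Visits 1 and 2, when subjects receive the first dose in the clinic".

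**The concern.** Read quickly, Section 7.1 and the synopsis place investigational product dosing in Stage 2 only, while Sections 7.4.1, 10.2 and 10.5 start it at Visit 1. On the first reading, a run-in event precedes dosing and is unrelated by rule. On the second, the investigator may grade it anywhere up to definitely related. The code is entered locally at about 80 sites, so sites could differ, and a rule written at analysis can move an event between periods but cannot recode it.

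Section 13.3 tabulates relationship by study group without a time limit. Run-in events in subjects later randomized could then be shown under an arm whose treatment they had not yet received. The stake is how clear the descriptive safety tables are. No efficacy result, sample size or type I error rate depends on this.

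**Working it through.** **1. Do the sections contradict each other?**

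| Place | What it describes |
|---|---|
| 7.1 | The sentence goes on, in parentheses, to name KPI-121 0.25% or vehicle in Stage 2. It therefore describes Stage 2 product and does not say that the run-in vehicle is something else. |
| Synopsis, dosage | Duration of the randomized treatment. Section 7.3 gives the same duration for each arm. |
| 7.4.1, 8.1 (criterion 3a), 10.2, Appendix 1 footnote b | Run-in vehicle as investigational product, marked as single-masked or Stage 1. |
| 7.4.2, 7.4.4, 13.3 | Post-randomization product, marked as double-masked or randomized. |
| 10.5 | The in-clinic dose at each of two visits counts toward that day's four. Each stage has its own product and so its own first dose. |

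These fit one reading: the run-in vehicle is investigational product, and the text usually marks which stage is meant. Section 7.4.1 lists the first instillation after consent and the Visit 1 examinations. Events in that interval are collected under 12.4 and precede all dosing, so the ground in 12.3 has a natural meaning that does not depend on Visit 2.

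**2. How much of the collection window is run-in?**

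Inputs: Stage 1 lasts 14 ± 1 days, so 13 to 15 (Section 7.4.2). Visit 4 is Day 15 + 2 counted from Day 1, so 14 to 16 days later (Section 7.4.4).

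- Lowest share: 13/(13 + 16) = 44.8%
- Nominal: 14/(14 + 14) = 50%
- Highest: 15/(15 + 14) = 51.7%

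**3. What if run-in events were counted by arm?**

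The documents give no adverse event rates, so all risks here are assumed. Let r be the run-in risk (equal in both arms in expectation, because it precedes randomization) and p the Stage 2 risk, with the two stages independent.

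- Tabulated risk = 1 − (1 − r)(1 − p)
- Difference between arms = (1 − r)(pA − pB), so a fraction 1 − r is kept
- With r = k·p for vehicle, the vehicle percentage is multiplied by 1 + k(1 − p)

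For vehicle p of 1% to 5%:

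| k | Multiplier, p = 5% | Multiplier, p = 1% |
|---|---|---|
| 0.25 | 1 + 0.25 × 0.95 = 1.238 | 1 + 0.25 × 0.99 = 1.248 |
| 0.5 | 1 + 0.5 × 0.95 = 1.475 | 1 + 0.5 × 0.99 = 1.495 |
| 1 | 1 + 0.95 = 1.95 | 1 + 0.99 = 1.99 |

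Here r runs from 0.25 × 1% = 0.25% to 1 × 5% = 5%, so the share of the risk difference kept runs from 99.75% down to 95.0%.

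For assumed Stage 2 risks of 10% and 5% (difference 5.0 points, ratio 2.00):

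| r | Active | Vehicle | Difference | Ratio |
|---|---|---|---|---|
| 1% | 1 − 0.99 × 0.90 = 10.9% | 1 − 0.99 × 0.95 = 5.95% | 4.95 points | 1.83 |
| 5% | 1 − 0.95 × 0.90 = 14.5% | 1 − 0.95 × 0.95 = 9.75% | 4.75 points | 1.49 |
| 10% | 1 − 0.90 × 0.90 = 19.0% | 1 − 0.90 × 0.95 = 14.5% | 4.5 points | 1.31 |

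Percentages rise and the ratio shrinks, while the difference moves little. None of this arises once tables are restricted to onset at or after the first randomized dose.

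**The case for a change.** The strongest case for a change has four parts.

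- **The Safety population selects subjects, not events.** This is correct, so 13.3 alone does not exclude run-in events. But it shows a post-randomization analysis is intended. The protocol also leaves detail to a separate SAP that is not in the text reviewed, where an onset cut would be ordinary content. Its absence from the plan as a whole cannot be shown.
- **A later cut cannot harmonize investigators' codes.** This is true of the codes themselves. However, only one product is in use at a time, and 12.4 records date and time of onset, so timing usually shows which product a code concerns.
- **A run-in event still present at Visit 2 may worsen on randomized treatment.** This stands. Section 12.4 lists no date of worsening, an onset cut would leave such an event in the run-in, and worsening could differ by arm. It is a narrow case, and the documents give no frequency for it.
- **Serious event reports in 12.5 ask for one product start date, and notice to all sites depends on relatedness.** This is a reporting matter. The same report asks for onset and a narrative. On the reading the text favours, a run-in serious event can be graded for relatedness, so the notice is not blocked by rule.

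**Conclusion.** No change is called for. The sections can be read together without contradiction. What remains is missing detail: 12.3 does not name its reference dose, and 13.3 states no onset cut. Analysts would normally fill this with a treatment-emergent rule in the SAP, applied from onset times that are already collected.

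About 45% to 52% of a completer's window from Visit 1 to Visit 4 precedes randomization, so the question is reasonable. But neither arm is favoured in expectation and the safety tables are descriptive. If run-in events were counted, the risk difference would keep 95.0% to 99.75% of its value at run-in risks of 0.25% to 5%, and 90% at a run-in risk of 10%. The inflated percentages and smaller ratio would arise only under that choice, which the Safety population wording points away from.

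The window shares come from the protocol's visit schedule. The rest assumes the stated event risks, independence between stages, and sensible handling of onset in the SAP.
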